3.6. Calculation of the sample size

Based on the sample calculation, the study by Soeding PF et al, 2011 (22) , which observed a drop in MAP under general anesthesia of approximately 30%, the study by Vincent S et al, 2005 (24) , which observed a decrease in MAP under sedation of 5.6%, and the study by Meidert et al 2017 (25) , which observed a decrease in SBP of 18 mmHg and 12 mmHg of MAP in the group with intermittent monitoring in relation to the group with continuous monitoring. Based on these data, a difference in mean total MAP between groups of 12 mmHg was used and therefore, considering the study power of 80% and alpha error of 0.025 by Bonferroni correction due to be divided into 4 groups, a total sample of 92 patients will be need, with standard deviation of the group with continuous monitoring of cardiac output of 10 mmHg and in the group standard monitoring of 15 mmHg. However, estimating that we may have losses, the final sample will reach 100 patients, so there will be 25 patients in each of the 04 groups.

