3.10. Data collect

After receiving an explanation about the procedures to be performed and signing the consent form, patients will be allocated into 4 groups as explained above using a table of random numbers. Data collected will be age, weight, height, race, gender, ASA, comorbidities, medications in use. During the surgical procedure, the analyzed data will be medications, infusion volume, blood components, vasopressor, anesthetic and surgical complications, anesthesia and surgery time.

In addition, systolic, diastolic and mean blood pressure, heart rate, cerebral O₂ saturation, peripheral O₂ saturation, axillary temperature, BIS value, cardiac index (in patients who will use clear sight) and et CO₂ (in patients who will be intubated) every 5 min intraoperatively and during post-anesthetic recovery (PAR) (27).

Postoperatively, the data analyzed will be: anesthetic recovery time, hospital stay, need to be referred to the intensive care unit (ICU), length of stay in the ICU and if the patient died. In addition, the visual numerical pain scale and the descriptive verbal pain scale will also be evaluated in the PVR and 24 hours after the procedure (28).

Sedation assessment will be performed using the intraoperative RASS scale for patients who are allocated to the sedation + interscalene brachial plexus block group and postoperatively for all groups. The values of the RASS scale are shown in table 1. The Confusion Management Method in the ICU (CAM-ICU) scale will be used to assess delirium, the table with the parameters used will be shown in figure 5 (29);(30).

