3.13. Data analysis

Categorical variables will be presented as absolute and relative frequencies.

Quantitative variables will be presented as mean and standard deviation or as median and interquartile range when appropriate. We will use the Kolmogorov-Smirnov test to assess the distribution pattern of continuous numerical variables.

Comparisons between general anesthesia + block and block + sedation will be performed, as well as comparisons between standard and continuous monitoring. Proportions will be compared using the Chi-square test or Fisher's exact test, if the assumptions for using the Chi-square are violated. Quantitative variables will be compared using the Mann-Whitney test or irregularly distributed Anova when appropriate.

Variables with repeated measurements will be analyzed by linear general multiple model (GLM) with Bonferroni correction for P values.

The association between explanatory variables and response will be evaluated using logistic regression models. Variables selected in the bivariate analyzes ($p<0.05$) and those considered clinically relevant will be submitted to multiple logistic regression analyses. Variables with substantial collinearity will be excluded. The result of logistic regression analyzes will be expressed as odds ratios and respective 95% confidence intervals.

All significance probabilities (P values) presented will be two-tailed. P values will be considered statistically significant when less than 0.05. *The Statistical Package for Social Sciences* software version 26.0 (SPSS Inc.®; Chicago, IL, USA) will be used to perform the analyses.

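### Section 3.6 sizes the trial at a Bonferroni alpha of 0.025, but Section 3.13 does not carry that level into the two MAP contrasts, and its only Bonferroni correction has no stated family

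*Combined protocol and SAP*

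**What the plan says.** Section 3.6 takes mean total MAP as the sizing variable: "a difference in mean total MAP between groups of 12 mmHg was used". It uses 80% power and an "alpha error of 0.025 by Bonferroni correction due to be divided into 4 groups", "with standard deviation of the group with continuous monitoring of cardiac output of 10 mmHg and in the group standard monitoring of 15 mmHg". The result is 92 patients, raised to 100 (25 in each of four groups) for losses.

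Section 3.13 names the comparisons by factor: "Comparisons between general anesthesia + block and block + sedation will be performed, as well as comparisons between standard and continuous monitoring". Quantitative variables go to Mann-Whitney or ANOVA, with no multiplicity correction mentioned. P values are two-tailed, and "P values will be considered statistically significant when less than 0.05". The level 0.025 does not appear in this section. Bonferroni appears once: "Variables with repeated measurements will be analyzed by linear general multiple model (GLM) with Bonferroni correction for P values".

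Section 3.10 has blood pressure, including MAP, recorded every 5 minutes.

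**The concern.** The level used to size the trial and the level used to judge it are linked by no sentence in the plan. MAP could be analysed in two ways. As one mean per patient it falls under the uncorrected Mann-Whitney/ANOVA rule at 0.05. As a series of 5-minute readings it falls under the repeated-measures model, with a Bonferroni correction whose family might be time points, the four groups or the two contrasts.

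On the first route, an unadjusted P of 0.03 on either contrast would be declared significant although the design set 0.025. On the second, two analysts could choose different families and reach different conclusions from the same data. The plan names no primary comparison that would settle the choice, so it could be made after the results are known.

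Section 3.6 also does not say which comparison its 80% power belongs to, and Section 3.13 does not say whether the contrasts are pooled over the other factor.

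**Working it through.** **Inputs.** From Section 3.6: difference 12 mmHg, SD 10 (continuous) and 15 (standard), alpha 0.025, power 80%, total 92. From Section 3.13: two-tailed tests, two named contrasts, threshold 0.05.

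**1. Reproduce the 92.** Two-sample t test with unequal variances, n per group:
- SE = sqrt((10² + 15²)/n) = sqrt(325/n).
- Welch df = (n − 1) × 325²/(100² + 225²) = 1.742 × (n − 1).
- Power comes from the noncentral t with noncentrality 12/SE.

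At n = 23, SE = 3.759, df = 38.3, the two-sided 0.025 critical value is 2.333 and the noncentrality is 12/3.759 = 3.192. Power is 80.1%. At n = 22 it is 78.0%. So 23 per group are needed, and 4 x 23 = 92, an exact match. The SDs are labelled by monitoring type and the 12 mmHg comes from a monitoring trial, so the comparison that fits is continuous versus standard monitoring within one technique (1A v 1B, 2A v 2B).

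**2. What the 0.025 corrects for.** 0.05/2 = 0.025, a correction for two comparisons. The same calculation for other families gives:

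| Family | Alpha | Per group | Total |
|---|---|---|---|
| Two comparisons | 0.025 | 23 | 92 |
| Four comparisons | 0.0125 | 28 | 112 |
| All six pairs of four groups | 0.0083 | 30 | 120 |

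Among these families, only the two-comparison correction gives 92.

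**3. Familywise error over the two contrasts**, both nulls true and tests independent:
- At 0.05 each: 1 − 0.95² = 9.75%.
- At 0.025 each: 1 − 0.975² = 4.94%.

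Simulating the 2x2 design under both nulls gives about 9.7% and 4.8%.

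**4. Results on which the two rules disagree.** The smallest significant observed monitoring difference is the critical t times SE, taking the planning SDs and, for the pooled rows, adjustment for technique or no technique effect:

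| Comparison | SE | At 0.05 | At 0.025 |
|---|---|---|---|
| 23 v 23 | 3.759 | 7.6 mmHg | 8.8 mmHg |
| 46 v 46 | 2.658 | 5.3 mmHg | 6.1 mmHg |

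A difference between the last two columns is significant under an uncorrected reading of Section 3.13 but not at the level in Section 3.6.

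**5. Power of the monitoring contrast for 12 mmHg**, same conditions:

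| Comparison | At 0.05 | At 0.025 |
|---|---|---|
| 23 v 23, within one technique | 87.5% | 80.1% |
| 46 v 46, pooled | 99.4% | 98.6% |

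At 46 v 46 and 0.025, 80% power corresponds to about 8.3 mmHg. With technique in the model, simulation gives 98.6% whatever technique effect is assumed.

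**6. If monitoring is tested within each technique.** The two monitoring tests at 0.025 use the whole 0.05. A technique test at 0.025 would be a third: 1 − 0.975³ = 7.3% if independent.

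**The case against.** The strongest defence is that the sections may already agree. MAP is measured repeatedly, so it can be read as belonging to the repeated-measures model, where a Bonferroni correction is promised. Bonferroni-adjusted P values judged at 0.05 are the same rule as unadjusted P values judged at 0.025 when the family has two members. This stands as far as it goes: the mismatch depends on the analysis route. It does not close the point, because the plan neither sends the sized quantity, a mean, down that route nor says that the family is the two contrasts.

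Two further replies have force. The powered comparison can be inferred from the SD labels and the source of the 12 mmHg. And splitting each technique by monitoring creates four groups and two within-technique monitoring comparisons, so 0.05/2 can be traced to that split. Both replies point to monitoring within technique. Section 3.13 names the contrasts by whole factor and mentions no such test, so the plan still has to say which is meant.

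The 9.75% is also a worst case: both nulls true and no correction applied. If monitoring has the planned 12 mmHg effect, an unadjusted pooled technique test at 0.05 rejects a true null only about 2.9% of the time in simulation, because the monitoring effect inflates the arm SDs.

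**Conclusion.** The point holds as an inconsistency between sizing and analysis that should be fixed before the data are analysed. With mean MAP as one value per patient, Section 3.13 does not apply the planned 0.025, and familywise error over the two contrasts is up to about 9.75% instead of 4.94%, assuming both nulls true and independent tests. With MAP in the repeated-measures model, control across the contrasts is unspecified.

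A reader might infer three stronger things that the documents do not support:
- That the sample size is miscalculated. It is not; 92 reproduces exactly at the stated inputs.
- That Section 3.13 flatly contradicts Section 3.6. That requires the single-value reading, which the reference to a mean makes plausible but the plan does not state.
- That four groups oblige a correction for six pairwise tests. Section 3.13 names two contrasts, and 0.025 fits two.

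The power figures rest on the planning SDs holding in both techniques. The pooled figures also require technique to be in the model or to have no effect. Section 3.6 gives no SD by technique, so it supports no stated power for the technique contrast.

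**What to change.** **Section 3.13.**
- State that technique and monitoring are each tested on mean intraoperative MAP at two-sided 0.025, or with P values Bonferroni-adjusted for these two contrasts and judged at 0.05.
- State that each contrast is pooled over the other factor, with both factors in the model.
- State that the Bonferroni family of the repeated-measures model includes these two contrasts, and what else it covers.
- If monitoring is instead to be tested within each technique, say so and state how the additional technique test is covered.

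**Section 3.6.**
- Give the reason for the correction as two comparisons instead of the division into four groups.
- State that the 80% is for monitoring at 23 v 23 within a technique.
- If the contrasts are pooled, restate monitoring power at 46 v 46 and two-sided 0.025, adjusted for technique, as 98.6% for 12 mmHg (80% for about 8.3 mmHg).
- Print no power for technique unless an SD for that contrast can be sourced.

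**Cost.** Wording only, and no extra patients for the pooled contrasts. Power for a 12 mmHg monitoring difference falls from 99.4% to 98.6% if pooled, or from 87.5% to the planned 80.1% within technique. Within technique, covering the technique test as well may require a further split of alpha, and that would need its own power check.

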3.14. Ethical aspects

This study will follow the ethical principles of research involving human beings of Resolution 196/96 of the National Health Council (BRASIL, 1996). Respecting the fundamental principles of autonomy, beneficence, non-maleficence, justice and equity. Research participants will sign the informed consent form (IC) for authorization. The project will only be executed after approval by the ethics and research committee (CEP).

5. SCHEDULE

ACTIVITY	DURATION	START	END
Literature review	24 months	Month 1	Month 24
Submission to CEP	6 months	Month 1	Month 6
Data collect	9 months	Month 7	Month 16
Data analysis	12months	Month 7	Month 19
Final writing	5 months	Month 19	Month 24

6. ANNEX OF FIGURES AND TABLES

	Target of RASS Values	RASS Description
+4	Combative	Combative, violent, imminent danger
+3	Very Busy	Pulls or removes tubes and catheters, aggressive
+2	Hectic	Frequent unintentional movements, struggling with the fan
+1	Restless	Anxious, apprehensive, but no aggressive or sudden movements
0	Alert and Calm	
-1	Sleepy	Not fully alert but keeps awake with voice (eyes open and in contact more than 10s)
-2	Light sedation	Briefly wakes up with voice (eyes open and in contact for less than 10s)
-3	Moderate sedation	Movements or eye opening with voice (but does not maintain eye contact)
-4	Deep sedation	Does not respond to voice but has eye movements or eye opening with physical stimulation
-5	Unresponsive	Does not respond to voice or physical stimulation

Table 1: RASS scale values

[figure not shown]
[figure not shown]

Figure 1: Flowchart of patient distribution.

Continuous monitoring

[figure not shown]

Figure 2: Flowchart of monitoring groups

Confusion Assessment Method in the ICU

[figure not shown]

Figure 3: Evaluation of the CAM-ICU scale. Figure taken from the study by Guenther et al 2010 (30).
